The primary objective of this study is to evaluate the efficacy of nebulized heparin administration in COVID-19. Our primary outcome will be defined as the mean PaO₂/FiO₂ ratio in the first 10 days of ICU stay. This is the gold standard for hypoxia monitoring in ARDS. Our secondary safety outcome will include clinically significant bleeding, defined as transfusion of red blood cells, required intervention for new-onset bleeding, or death attributed to bleeding during the study period. Additional outcomes will include incidence of VTE, time on mechanical ventilation, ICU duration, and overall mortality.

Study Design: Describe the study design (e.g., single/double blind, parallel, crossover, etc.). Indicate whether or not the subjects will receive placebo medication at some point in the research procedures. Also, indicate whether or not the subjects will be randomized in this study. You may reference sponsor's protocol pages and attach as an appendix in the E-IRB "Additional Information" section, however, a summary paragraph must be provided in the text box below. (Including the study design table from a sponsor's protocol is helpful to IRB members.)

Community-Based Participatory Research: If you are conducting community-based participatory research (CBPR), describe strategies for involvement of community members in the design and implementation of the study, and dissemination of results from the study.

Research Repositories: If the purpose of this submission is to establish a Research Repository (bank, registry) indicate whether the material you plan to collect would or would not be available from a commercial supplier, clinical lab, or established IRB approved research repository. Provide scientific justification for establishment of an additional repository collecting duplicate material. Describe the repository design and operating procedures. For relevant information to include, see the UK Research Biospecimen Bank Guidance [PDF] or the UK Research Registry Guidance [PDF]

We propose a randomized, controlled pilot study of patients admitted with confirmed COVID-19 receiving mechanical ventilation for ARDS (paO₂/FiO₂ ratio =300) within 48 hours. Enrollment will occur by the ICU research team who perform daily review for study enrollment. Patients will be randomized to nebulized heparin (25,000 units in 3 mL sodium chloride [NaCl] every 6 hours) versus

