placebo (5 mL nebulized NaCl every 6 hours) for 10 days or until successful ventilator wean. Drugs will be dispensed by investigational drug services. Patients will be excluded for a history of heparin allergy, terminal status as determined by attending physician, history of thrombosis (prior VTE or cardiovascular event), high risk of bleeding (platelet count < 50,000/ μ L or international normalized ratio > 1.5), or active bleeding. Monitoring will include daily ventilator parameters, complete metabolic panels, and complete blood counts, as well as hourly vital signs as part of standard care. The MICU also has an actively enrolling biobank with respiratory samples which we will use to assess viral load. Additional samples will be collected for coagulation (protein S, thrombin, and histone) monitoring, at baseline, 72 hours, and day 10. Laboratory results, medication administration, and vital sign data will be collected up until 10 days of ICU admission or discharge. Mortality, length of stay, and mechanical ventilation duration will be collected for the entire hospital stay. Based on expected baseline $\text{paO}_2/\text{FiO}_2$ ratio of 118 mmHg, we calculate that we need a sample size of 46 patients (n=23 per group) to detect a 15% improvement in $\text{paO}_2/\text{FiO}_2$ ratio, assuming an alpha of 0.05 and power of 80%. (22)

Attachments

[Back to Top](#)

Study Population: Describe the characteristics of the subject population, such as anticipated number, age range, gender, ethnic background and health status. Identify the criteria for inclusion and exclusion. Explain the rationale for the use of special classes such as fetuses, pregnant women, children, institutionalized, adults with impaired consent capacity, prisoners, economically or educationally disadvantaged persons or others who are likely to be vulnerable.

If women or minorities are included, please address how the inclusion of women and members of minority groups and their subpopulations will help you meet your scientific objectives. Exclusion of women or minorities requires clear and compelling rationale that shows inclusion is inappropriate with respect to the health of the subjects or that inclusion is inappropriate for the purpose of the study. Cost is not an acceptable reason for exclusion except when the study would duplicate data from other sources. Women of childbearing potential should not be excluded routinely from participation in clinical research.

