Provide the following information:

- A description of the subject selection criteria and rationale for selection in terms of the scientific objectives and proposed study design;
- A compelling rationale for proposed exclusion of any sex/gender or racial/ethnic group;
- The proposed dates of enrollment (beginning and end);
- The proposed sample composition of subjects.

You may reference grant application/sponsor's relevant protocol pages and attach as an appendix using the below attachment button, however, a summary paragraph must be provided in the text box below.

Patients admitted with confirmed COVID-19 receiving mechanical ventilation for ARDS ($\text{paO}_2/\text{FiO}_2$ ratio =300) will be included.

Patients will be excluded for the following:

- Allergy to heparin
- Any history of heparin-induced thrombocytopenia
- High risk of bleeding (platelet count < 50,000/ μ L or international normalized ratio > 1.5)
- Patients with known bleeding disorders (i.e. hemophilia or von Willebrand Disease)
- Active bleeding
- Pulmonary bleeding during this hospital admission (Pulmonary bleeding is frank bleeding in the lungs, trachea or bronchi with repeated hemoptysis, or requiring repeated suctioning, and temporally associated with acute deterioration in respiratory status)
- Neurosurgical procedures during this hospital admission or such procedures are planned
- Epidural catheter in place
- Any history of intracranial, spinal or epidural hemorrhage
- Tracheostomy in place
- Cervical spinal cord injury associated with reduced long-term ability to breathe independently
- Spinal or peripheral nerve disease with a likely prolonged reduction in the ability to breathe independently
- Receiving extra-corporeal membrane oxygenation or continuous renal replacement therapy
- Usually treated with hemodialysis or peritoneal dialysis for end-stage renal failure
- Death is deemed imminent or inevitable or there is an underlying disease with a life expectancy of fewer than 90 days
- Pregnant or might be pregnant.
- Objection from the treating clinician
- Consent refused by the patient or substitute decision maker.
- History of thrombosis (VTE or cardiovascular event)

Attachments

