The following will be recorded from standard of care documentation: demographics (age, sex, race, past medical history), chief complaint, past medical history, blood gases, medications, and transfusions administered and dosing, mechanical ventilation parameters, complete blood counts, complete metabolic panels, and vital signs. Patient outcomes including in-hospital mortality, Murray Lung Injury Score, ICU and hospital length of stay, the incidence of venous thromboembolism, the incidence of pulmonary embolism, the incidence of clinically significant bleeding, and duration of mechanical ventilation. Lab values for coagulation (protein S, thrombin, and histone) monitoring with an additional blood draw at baseline, 72 hours, and day 10.

Attachments

Resources: Describe what resources/facilities are available to perform the research (i.e., staff, space, equipment). Such resources may include a) staffing and personnel, in terms of availability, number, expertise, and experience; b) psychological, social, or medical services, including counseling or social support services that may be required because of research participation; c) psychological, social, or medical monitoring, ancillary care, equipment needed to protect subjects; d) resources for subject communication, such as language translation services, and e) computer or other technological resources, mobile or otherwise, required or created during the conduct of the research. Please note: Some mobile apps may be considered mobile medical devices under FDA regulations (see [FDA Guidance](#)). Proximity or availability of other resources should also be taken into consideration, for example, the proximity of an emergency facility for care of subject injury, or availability of psychological support after participation.

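### Does the 80% power claim fail because it starts from a baseline P/F of 118 mmHg and gives no SD for the 10-day mean?

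*Protocol*

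**What the plan says.** The Objectives text of the Research Description opens: "The primary objective of this study is to evaluate the efficacy of nebulized heparin administration in COVID-19". It defines the primary outcome as the mean PaO2/FiO2 "ratio in the first 10 days of ICU stay".

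The Study Design text begins: "We propose a randomized, controlled pilot study of patients admitted with confirmed COVID-19". It ends with the sample size, which starts from an expected baseline P/F "ratio of 118 mmHg, we calculate that we need a sample size of 46 patients (n=23 per group) to detect a 15% improvement in" P/F, "assuming an alpha of 0.05 and power of 80"%. A literature citation follows (reference 22, by its title a study of respiratory mechanics in COVID-19 and non-COVID-19 ARDS).

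The word baseline qualifies only the 118 mmHg. The text does not say whether the 15% is a difference between arms in the 10-day mean or a change from baseline. It gives no SD, no test and no sidedness.

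**The concern.** A sample size for a difference in means needs an SD, and the protocol has none. The only mean quoted is a baseline value, while the variable to be tested is a 10-day average. That average can have a different mean and a different spread. Averaging repeated values reduces the spread. Diverging clinical courses increase it, and so do averages that rest on fewer days, since "medication administration, and vital sign data will be collected up until 10 days of ICU admission or discharge".

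This sentence is the protocol's only statement of what the trial can detect. If the 10-day mean varied much more than the planners assumed, 80% power for a 15% gain would be an overstatement, and a reader might take a non-significant result as evidence against a 15% gain when it is not.

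**Working it through.** **Inputs from the protocol (Study Design):** anchor mean 118 mmHg; effect 15%; alpha 0.05; power 80%; 23 per group. **Assumed, because the protocol does not say:** two-sided test, unadjusted two-sample t-test, common SD, and the 15% read as a difference between arms.

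**Reproducing the 46.** This cannot be done forwards without an SD. It can be solved backwards for the SD at which 23 per group gives exactly 80% power.

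- Difference on the stated anchor: 0.15 × 118 = 17.7 mmHg.
- Normal approximation: detectable standardised difference = (1.960 + 0.842) × √(2/23) = 2.802 × 0.2949 = 0.826. Largest SD = 17.7 / 0.826 = 21.4 mmHg; CV = 21.4 / 118 = 18.2%.
- Noncentral t, 44 degrees of freedom: 0.8447. Largest SD = 17.7 / 0.8447 = 20.95 mmHg; CV = 0.15 / 0.8447 = 17.8%.

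So 23 per group is what an SD of about 21 mmHg would produce. The planners may have used such a value, taken from their source or from elsewhere; the protocol does not show it.

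**Does the baseline anchor matter?** If the 15% is relative to the control arm's 10-day mean, the mean cancels, since the limit is 0.15 / 0.8447 whatever the mean. It stays at 17.8% for control means of 118, 150, 180 and 200 mmHg. Only if a fixed 17.7 mmHg were intended would a higher 10-day mean tighten the limit: 20.95 / 150 = 14.0% and 20.95 / 180 = 11.6%. Those two means are illustrations. The protocol expresses its effect as a percentage, not in mmHg.

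**How far do the unstated choices move the limit?**

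| Reading | CV limit for the 15% claim |
|---|---|
| Two-sided, unadjusted | 17.8% |
| One-sided 0.05, unadjusted (0.7448 SD) | 20.1% |
| Two-sided, baseline-adjusted, assumed r = 0.5 | 20.5% |
| Two-sided, baseline-adjusted, assumed r = 0.7 | 24.9% |

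The protocol excludes none of these.

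**Power for a 15% gain on both sides of the limit** (23 per group, two-sided, unadjusted t-test; every CV is assumed):

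| CV of the 10-day mean | 14% | 15% | 17% | 18% | 20% | 25% | 30% |
|---|---|---|---|---|---|---|---|
| Power | 94% | 91% | 83% | 79% | 70% | 51% | 38% |

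Assumed CVs of 18% and above, taken alone, would suggest a shortfall. CVs of 17% and below suggest power to spare. The protocol supports neither choice.

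**What the trial will report in any case.** The 95% confidence interval for the difference between arms has half-width t(44) × √(2/23) = 2.015 × 0.2949 = 0.594 times the observed SD. Whether the data speak against a 15% gain is read from that interval, not from the planning sentence.

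**The case for a change.** The strongest case for a change is that the protocol does make a formal power claim, attached to an efficacy objective, and so cannot rely on being a pilot or on a statistical analysis plan that may hold the details. The claim depends on a CV of about 18% or less that is nowhere stated. Wording such as 80% power for about 0.84 SD of the 10-day mean would be true for any SD and would cost one sentence. Adjusting for baseline P/F could add precision from data already collected: entry is defined for "Patients admitted with confirmed COVID-19 receiving mechanical ventilation for ARDS" with a P/F threshold, and the Data Collection list includes "blood gases, medications, and transfusions administered and dosing, mechanical ventilation parameters". At an assumed CV of 25%, adjustment would raise power for a 15% gain from 51% to 63% at an assumed r of 0.5.

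Part of this stands. The sentence is incomplete, the 15% is not explicitly tied to the 10-day mean, and the conditional limit of about 18% is correct. A fuller sentence would be better reporting.

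The rest does not require a change. An unverifiable figure is not a wrong one, and the new wording would leave the 46 patients, the outcome and the analysis as they are. Test, sidedness and covariates are commonly fixed in a statistical analysis plan, which may exist but is not available here. The gain from adjustment depends wholly on the assumed correlation: at r = 0.3 and a CV of 25%, power rises only from 51% to 55%. The outcome window is counted in ICU days rather than from randomisation, so a pre-randomisation P/F may already form part of the outcome. That needs thought before the covariate is called free.

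**Conclusion.** No change to the plan follows. The protocol leaves out the SD, test and sidedness behind a cited calculation, and labels only its anchor value as baseline. For an unadjusted two-sided t-test with a common SD, the 80% power claim for 15% holds if the CV of the 10-day mean P/F is at most 17.8% (SD 21.0 mmHg at a mean of 118). One-sided testing or baseline adjustment at assumed correlations of 0.5 to 0.7 relaxes this to roughly 20% to 25%. The true CV is not in the protocol, so the claim could be conservative or optimistic. With the 15% taken relative to the control mean, the baseline anchor has no effect on the sample size.

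This is a minor reporting gap. A reader can translate 23 per group into 0.845 SD without help from the authors, and the confidence interval at the end will show what the trial could and could not exclude. The conclusion would change if a sourced SD for the 10-day mean clearly above the limit came to light; nothing in the protocol supplies one.

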**Check All That Apply**

Informed Consent Form (and/or Parental Permission Form)
 Assent Form
 Cover Letter (for survey/questionnaire research)
 Phone Script
 Informed Consent/HIPAA Combined Form
 Debriefing and/or Permission to Use Data Form
 Sponsor's sample consent form for Dept. of Health and Human Services (DHHS)-approved protocol
 Stamped Consent Doc(s) Not Needed

Attachments

Attach Type	File Name
Informed Consent/HIPAA Combined Form	Informed Consent RedCap.pdf
Informed Consent/HIPAA Combined Form	Informed Consent 03.24 Clean.pdf

 Request for Waiver of Informed Consent Process

If you are requesting IRB approval for waiver of the requirement for the informed consent process, or alteration of some or all of the elements of informed consent (i.e. medical record review, deception research, or collection of biological specimens), complete Section 1 and Section 2 below.

Note: The IRB does not approve waiver or alteration of the consent process for greater than minimal risk research, except for planned emergency/acute care research as provided under FDA regulations. Contact ORI for regulations that apply to single emergency use waiver or acute care research waiver [contact]).

SECTION 1.

Check the appropriate item:

I am requesting waiver of the requirement for the informed consent process.

I am requesting alteration of the informed consent process.

If you checked the box for this item, describe which elements of consent will be altered, and/or omitted, and justify the alteration.

SECTION 2.

The IRB may consider your request provided that **all** of the following conditions apply to your research and are appropriately justified. Explain in the space provided for each condition how it applies to your research.

a) The research involves no more than minimal risk to the subject.

The electronic medical record will be utilized to determine patient eligibility. No component of this aspect of the study is greater than minimal risk. While this is a prospective study to placebo versus nebulized heparin, informed consent will be obtained prior to enrollment.

b) The rights and welfare of subjects will not be adversely affected.

To protect the confidentiality of the patient, data will be housed in a password-protected master list spreadsheet. Once data has been collected, this sheet, linking the medical record number and unique study number will no longer be used. Data will be analyzed and reported in a de-identified form.

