Patients will be screened for eligibility by a member of the research team. If a patient meets eligibility, then a team member will approach the LAR for informed consent. After enrollment, the patient will be randomized via an online randomization generator to either nebulized heparin (25,000 units in 3 mL sodium chloride [NaCl] every 6 hours) or placebo (5 mL nebulized NaCl every 6 hours) for 10 days or until successful ventilator wean. The nurse will be approached for a 10 mL blood draw to be performed at baseline, 72 hours, and day 10 to assess protein S, thrombin, and histone in the [name] laboratory (BBSRB B306-15 and B306-16). The study team will collect the blood samples. Up to 10 mL of blood will be drawn each time for a maximum of 30 mL total, collected in citrate-containing tubes. Deidentified data will be collected via RedCap from the standard of care charting. Upon study completion, deidentified data will be sent to the statistician for analysis.

Attachments

Data Collection: List the data or attach a list of the data to be collected about or from each subject (e.g. interview script, survey tool, data collection form for existing data).

If the research includes survey or interview procedures, the questionnaire, interview questions or assessment scales should be included in the application (use attachment button below).

The data collection instrument(s) can be submitted with your application in draft form with the understanding that the final copy will be submitted to the IRB for approval prior to use (submit final version to the IRB for review as a modification request if initial IRB approval

was issued while the data collection instrument was in draft form).

Note: The IRB approval process does not include a statistical review. Investigators are strongly encouraged to develop data management and analysis plans in consult with a statistician.

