intensive care unit and subject to the intensive monitoring required from the baseline care of such a population. Once the database has been completed from information collected, identifiable information will be removed and replaced with a subject ID number. The PI will maintain a logbook of the ID number with patient identifiers in a locked cabinet in a locked office. If clinically significant bleeding occurs during drug treatment, defined as transfusion of red blood cells thought to be secondary to investigational drug or required intervention for new-onset bleeding secondary to investigational drug, the drug will be automatically stopped.

Benefit vs. Risk: Describe potential benefits to the subject(s); include potential benefits to society and/or general knowledge to be gained. Describe why the risks to subjects are reasonable in relation to the anticipated benefit(s) to subjects and in relation to the importance of the knowledge that may reasonably be expected to result. If you are using vulnerable subjects (e.g., impaired consent capacity, pregnant women, etc...), justify their inclusion by describing the potential benefits of the research in comparison to the subjects' vulnerability and the risks to them. For information about inclusion of certain vulnerable populations, see the IRB/ORI Standard Operating Procedure for Protection of Vulnerable Subjects [C3.0100] [\[PDF\]](#).

We do not know if subjects in this group will benefit directly, but hypothesized benefits of the use of nebulized heparin include decreased length of stay and decreased lung injury scores. Risks are outlined in the informed consent document and notably include the risk of bleeding. Given the mortality rate in patients with ARDS secondary to COVID-19, there may be patients that benefit from this drug despite the minimal risks. We have attempted to use the literature to guide our protocol to reflect those patients most likely to benefit.

Available Alternative Treatment(s): Describe alternative treatments and procedures that might be advantageous to the subjects, should they choose not to participate in the study. This should include a discussion of the current standard of care treatment(s).

There are no alternative treatments. Patients enrolled will continue to receive standard of care therapies per the discretion of the primary team. Thromboprophylaxis is permitted per standard of care. Patients who require systemic anticoagulation will be excluded from this study.

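### Heparin in 3 mL against 5 mL of saline, with no blinding level stated: the placebo is not shown to be matched, so bedside staff may be able to tell the arms apart

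*Protocol*

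**What the plan says.** The intervention is described twice in the protocol's Research Description, with the same figures. Study Design gives the active arm as "nebulized heparin (25,000 units in 3 mL sodium chloride [NaCl] every 6 hours) versus" and the control as "placebo (5 mL nebulized NaCl every 6 hours) for 10 days or until successful ventilator wean". Research Procedures repeats both: "nebulized heparin (25,000 units in 3 mL sodium chloride [NaCl] every 6 hours) or placebo (5 mL nebulized NaCl every 6 hours".

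The form's Study Design prompt asks the investigator to "Describe the study design (e.g., single/double blind, parallel, crossover, etc". The reply opens "We propose a randomized, controlled pilot study of patients admitted with confirmed COVID-19" and describes a placebo arm, but gives no blinding level. The consent-waiver justification (Section 2, item a) also presents the comparison as placebo-controlled: "While this is a prospective study to placebo versus nebulized heparin".

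Other statements that bear on the point:

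- Objectives: the primary outcome is the mean PaO2/FiO2 "ratio in the first 10 days of ICU stay". The safety outcome includes deaths attributed to bleeding.
- Available Alternative Treatment(s): "Patients enrolled will continue to receive standard of care therapies per the discretion of the primary team".
- Safety Precautions: study drug is stopped when a transfusion or a bleeding intervention is put down to the study drug.
- Study Design: the investigational drug service dispenses. No masking step is described.
- Study Drug Information: a study drug form is attached, but its content is not part of the text at hand.

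**The concern.** A saline placebo is normally used so that those who treat and assess the patient do not know the arm. That needs products that look and behave alike, and a statement of who is kept unaware. Here the stated volumes differ and the second element is absent. A nurse or respiratory therapist who fills or watches the nebuliser could notice a difference in volume and learn which volume belongs to which arm.

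Three elements of the trial depend on people at the bedside:

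- FiO2, the denominator of the primary outcome, is a ventilator setting. The protocol leaves standard care to the primary team. That this covers FiO2 is my inference, though an ordinary one.
- Dosing ends at a successful wean, which is a clinical decision. Time on mechanical ventilation is also an outcome.
- Whether a death is attributed to bleeding is a judgement, and it counts in the safety outcome.

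The decision to stop study drug after a bleed also turns on attribution to the drug. Someone who knew that the patient was receiving saline might judge that differently. This affects who stays on treatment, not how the safety outcome is counted.

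**Working it through.** **Inputs.** From Study Design and Research Procedures: heparin dose 25,000 units; volume stated with it 3 mL; placebo volume 5 mL. Not stated in the text at hand: heparin stock strength, the volume V that the heparin contributes, and the final nebulised volume in the active arm.

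**Reading 1: 3 mL is the final volume.** Difference per dose = 5 − 3 = 2 mL. Ratio = 5 / 3 = 1.67. The placebo is visibly larger.

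**Reading 2: 3 mL is diluent, and the heparin is added to it.** Active total = 3 + V, with V = 25,000 / strength. A match needs 3 + V = 5, so V = 2 mL and strength = 25,000 / 2 = 12,500 units/mL. The strengths below are assumptions that show the range:

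| Assumed strength (units/mL) | V (mL) | Active total (mL) | Placebo (mL) | Placebo minus active (mL) |
|---|---|---|---|---|
| 25,000 | 1.0 | 4.0 | 5 | +1.0 |
| 20,000 | 1.25 | 4.25 | 5 | +0.75 |
| 12,500 | 2.0 | 5.0 | 5 | 0 |
| 10,000 | 2.5 | 5.5 | 5 | −0.5 |
| 5,000 | 5.0 | 8.0 | 5 | −3.0 |

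Under this reading the placebo may be larger than, equal to or smaller than the active product. Only one strength gives equality, and the text does not name it.

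**Blinding.** I set the prompt beside its answer. The prompt offers single or double blind as examples. The answer states randomisation, control, placebo, dose and dispensing, and does not state who is blinded. Research Procedures adds an online randomisation generator, again with no masking step. Elsewhere the term double-blind occurs only in the title of a cited trial in the reference list.

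**Effect on the result.** The document gives nothing from which to calculate how far knowledge of the arm would move the PaO2/FiO2 ratio, or in which direction. I give no figure for bias.

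**The case against.** The strongest reply is that no mismatch is established. The phrase about 3 mL of sodium chloride can fairly be read as naming the diluent, and a 5 mL placebo could then be a deliberate match. The study drug form and the consent documents are attached but not at hand, and either might set out preparation and masking. The investigational drug service dispenses and may well mask the product. All of this stands, and it is why the point is that the placebo is not shown to be matched, and not that it is unmatched.

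A reader might go further and infer any of the following. The documents do not support them.

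- *That the protocol contradicts its own double-blind design.* It never claims to be blinded, so there is no contradiction. Nor does it say that the trial is open.
- *That the blind will be broken.* This needs concealment to be intended, the final volumes to differ, and staff both to see the difference and to know which volume is which. No section establishes all of these.
- *That the transfusion and intervention components of the safety outcome are biased through attribution.* Under Objectives these are counted without asking whether the study drug was the cause. The attribution wording is in Safety Precautions and governs only stopping the drug.
- *That the primary outcome would shift in a known direction.* It is a ratio built from measured blood gases and charted settings, so a change in FiO2 does not by itself move it one way.

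The reply does not remove the point. Under either reading, someone who follows the protocol text cannot tell whether the two products match or who should be unaware of the arm. Both are matters of design and conduct that are not ordinarily left to a statistical analysis plan.

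**Conclusion.** The point holds as a cheap improvement that should be made. The stated volumes differ by 2 mL per dose if 3 mL is the final volume. If 3 mL is diluent only, the totals agree solely at 2 mL of heparin, which the text does not specify. With the blinding prompt also unanswered, bedside staff may be able to tell the arms apart in a trial whose primary outcome, end of dosing and bleeding-attributed deaths are open to clinician influence.

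The conclusion rests on the protocol text alone. It would reduce to a request to copy wording across if the study drug form already fixes a matched final volume and masking. The size and direction of any resulting bias are unknown.

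**What to change.** In Study Design and Research Procedures, specify one identical final nebulised volume for both arms: heparin plus diluent made up to that volume, and sodium chloride alone to the same volume for placebo. The sponsor chooses the figure. Have the investigational drug service, which already dispenses, supply both in identical coded containers. Answer the blinding prompt by stating that bedside staff and outcome collectors are blinded. If the study drug form already settles any of this, carry it into the protocol text.

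The cost is protocol wording plus minor pharmacy preparation and coding work. No patients or study procedures are added.
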